6.2. Phase Three - Ancillary Sub-Studies

6.2.1 Cost Effectiveness Evaluation

Background

A decision analytical model will be developed during Phase One of the MATTS project to inform the expert consensus process in defining an appropriate reference standard and developing a clinically and cost-effective new triage tool. In Phase Three, an economic evaluation will be performed to evaluate the costs incurred and expected benefits of a fully implemented new national major trauma triage tool strategy, compared to other triage tools/strategies. The overall aim is to structure and parameterise a model that reflects the costs and consequences of different pre-hospital triage strategies in patients with major trauma.

Decision problem and Model scope

The scope of the decision model is informed by the decision problem specified in the HTA commissioning brief and the base case principles for economic evaluations outlined in the NICE Guide to the Methods of Technology Appraisal.[39] The model setting will be an English major trauma network. Any triage tool strategy that could be feasibly be implemented in the NHS will be considered. The model will take the perspective of the English NHS, and thus include direct medical costs and costs arising from personal and social services. As major trauma may result in death or long term disability, costs and consequences will be examined over a life-time horizon. In line with the NICE reference case productivity losses, costs to patients and families, and resource use in non-health sectors will not be considered.

Model structure and study population

An individual patient simulation will be developed to estimate the clinical and costeffectiveness of different pre-hospital major trauma triage strategies.[40] A patient level model was chosen over a cohort model to fully explore sub-groups and non-linearity in results arising from heterogeneous major trauma populations. The precise model structure will be determined after conceptual modelling, literature review and in conjunction with clinical experts. Key events may include triage decisions, secondary transfer and definitive care, hospital management, and major trauma-related death and disability. A base-case population of individuals representative of patients attended by EMS following injury will be investigated. Patient characteristics will be determined by representative data sources e.g. existing ambulance service and TARN data. A priori subgroups of interest will include children and elderly patients; isolated traumatic brain injury versus non-brain injury; and blunt versus penetrating trauma.

Model parameterisation

Model inputs will be informed by literature reviews, routine official data sources at low risk of systematic error, and prospective MATTS data. Evidence synthesis will be performed according to best practice when required.[41] Where relevant and unbiased published evidence is unavailable, expert opinion will be formally elicited.[42] Each model input will be assigned an average or most likely value, and a probability distribution representing a credible range and the relative likelihood of possible values for the uncertainty in this estimate defined. Distributional choices will be chosen based on theoretical considerations, logical constraints, and the parameter estimation process. Where the data exists, correlation between model inputs, costs and outcomes will be accounted for using appropriate co-

MATTS Study

variances. Outcomes will include death, disability and quality-adjusted life years (QALYs) accrued by each triage tool strategy. Costs for EMS management, initial hospital assessment and ongoing hospital management will be estimated using NHS reference costs. Appropriate rehabilitation and long term care costs will also be assigned.

Model implementation and analysis

Simul8 software (Simul8 Corporation, Boston, USA) will be used to track the progression of heterogeneous patients with the accumulating history of each individual determining: the probability of, and time to, events; costs; and health outcomes. Internal testing will be performed throughout model development to ensure that mathematical calculations accurately represent model specifications and are correctly implemented. Debugging techniques will include: null and extreme input values; setting equal values across strategies; fixed distributions; and code breaks with line by line checking of syntax. The model will be also be independently verified by a second modeller. Model validation will be performed by comparing model outputs with published estimates from the literature.[40]

Outcomes

The main outcome measure for the Phase 3 economic modelling is the incremental costeffectiveness ratio (ICER) for each triage tool strategy.[40] A full incremental analysis will be conducted comparing the new implemented triage tool with all other feasible strategies, according to established principles of strong and extended dominance. The ICER will be compared to a maximum acceptable ICER range of £20,000 to £30,000 per QALY gained, in line with decision making processes by NICE.[61] An initial base case deterministic analysis, with parameters fixed at their mean or mostly likely values, will estimate the mean expected costs and QALYs gained per patient for each triage strategy. In order to account for the uncertainty in model inputs and non-linearity within the model a base case probabilistic sensitivity analysis (PSA) will also be conducted using Monte Carlo simulation to randomly sample from the inverse cumulative distribution function of each model parameter's probability density function.[43] Mean ICERs for each management strategy, calculated from the average expected costs and effects over all model runs, will be recalculated and compared with cost-effectiveness thresholds to inform adoption decisions.

Model uncertainty due to variability, heterogeneity, parameter uncertainty and structural uncertainty will be fully explored in sensitivity analyses. Investigation of variability arising from random differences between individuals with similar characteristics is facilitated by the individual patient sampling design. Heterogeneity will be examined in the pre-specified sub-group analyses. Univariate, threshold and scenario sensitivity analyses will be performed on model parameters thought to be important or uncertain. Structural uncertainty in methodological choices and assumptions (e.g. varying the discount rates for costs and effects) will also be also examined. The exact sensitivity analyses will be formulated post hoc informed by input from an expert clinical group, model structuring, evidence synthesis and emerging results.

Value of information analysis will also be conducted to examine if further research into the cost-effectiveness of the strategies is an efficient use of resources from the health care system perspective, and determine the overall gain associated with: removing all uncertainty from the decision problem (Expected Value of Perfect Information); removing all uncertainty from a subset of parameters (Expected Value of Partial Perfect Information); and if these values are sufficiently large, the expected value of conducting future research assuming finite sized trials (Expected Value of Sample Information).[44] The exact focus of such analyses would be determined during the research but candidate studies could include a cluster-randomised trial of new versus existing triage tools, or the collection of further evidence to validate the adoption decision advocated by current evidence.

6.2.2 Acceptability and usability of implemented triage tool

The acceptability and usability of the triage tool implemented in the Phase Three service evaluation study will be investigated using mixed qualitative and quantitative methods.[45] Barriers to triage tool implementation, and targets to improve future performance, will also be identified. Three approaches will be used:

- Trauma triage tool use: An important question is, of all eligible trauma patients, in how many cases was the tool used? To assess this we will measure what proportion of eligible patients (identified using the MATTS expert consensus definition) were recorded as assessed using the trauma triage tool in the ambulance service records in each study area. Overall and individual service rates will be calculated to establish if there are any between service differences. For cases identified as eligible but where the tool was not applied we will conduct descriptive analyses of patient, incident type and injury variables to assess if there are any common characteristics which may help further refine the tool.
- Online Survey: We will conduct an electronic survey of all participating clinicians using the tool in Phase Three to elicit their views on the usefulness and practical application of the tool. [46] Study information will be provided at the beginning of the survey and informed consent for completion and data collection obtained. A questionnaire will be designed using open and closed questions to explore factors including ease of use; relevance of criteria; confidence in decisions; improvement in function compared to previous tools; redundant or missing criteria; design or content issues that could further improve the tool. Closed questions with multiple choice answers will be coded and analysed using descriptive statistics. Frequencies of responses will be tabulated and presented as aggregated data for all services combined and individual services. Open questions using free text responses will be transcribed in to tables and data scrutinised to identify within and between question themes to identify which elements of the tool worked well, and which could be improved with further refinement. The findings of the survey will be triangulated with the themes identified during the Phase One clinician focus groups to map whether potential barriers and facilitators have been adequately addressed or if there are still unresolved issues that require further work.[47]
- Dissemination and development workshop: We will conduct a workshop with a range of stakeholders including clinicians (pre-hospital and hospital), patients, commissioners, service providers, senior NHS management and policy makers. The results of the Phase Two and Phase Three will be presented and will summarise what has worked well and where there are still potential gaps in successful implementation. We will then facilitate a structured discussion of the findings and explore issues of acceptability, usefulness and suggestions for further improvement from different stakeholder perspectives.[48] Outputs from these discussions will be presented by each group to all participants and collated as themes. Where potential areas for improvement are identified a consensus decision will be sought on importance and priority for subsequent further development. The findings from each of these activities will be collated and developed in to a practical "toolkit" to support further implementation of the trauma triage tool in other services if the tool is established as a viable alternative to existing tools.

7. Study supervision

Study Steering Committee

A Study Steering Committee will be convened during study set up. This group will provide overall supervision of the MATTS project in general, and the Phase 2 validation and Phase 3 service evaluation studies specifically, on behalf of the trial sponsor (University of Sheffield) and funder (National Institute of Health Research, NIHR). The SSC will ensure that the study is conducted according to principles of Good Clinical Practice (GCP), with specific tasks including:

- Approval of the study protocol
- Review of study progress
- Monitoring adherence to study protocol
- Ensuring patient safety
- Consideration of new information relevant to the research question
- Scrutiny of protocol amendments and extension requests
- Recommend appropriate actions such as changes to the protocol, additional patient information, stopping or extending the study.

The composition of the SSC is detailed in Table 3. The SSC will receive information from the Project Management Group and the DMEC. SSC meetings will be convened by the CI approximately annually. Representatives of the trial sponsor and funder may also be invited to participate. The SSC chairperson will provide advice to the CI, sponsor (University of Sheffield), host institutions (Ambulance services and trauma networks), and funder (NIHR). The SSC will have the power to prematurely close the study if necessary due to safety concerns, futility, or lack of convincing clinical effectiveness.

Table 3. Composition of Study Steering Committee

SSC roles	DMEC roles
Members:	Members:
Independent chair	Independent chair
Lay representative	Independent clinician
Independent statistician	Independent statistician
Independent paramedic	
Independent clinician	
Chief Investigators	

Project Management Group

A Project Management Group (PMG) will oversee day-to-day management of the MATTS validation and service evaluation studies, in accordance with CTRU SOP GOV001. Specific roles will include:

- Ensuring adherence with the study protocol
- Ensuring ethical and GCP standards are met
- Monitoring data quality
- Developing and reviewing paperwork
- Responding to queries from the host institutions

- Developing the study protocol in response to operational challenges
- Review of results
- Dissemination of study findings

The PMG will comprise the CI, study manager, co-investigators, trial statistician, research paramedics, ambulance service Research and Development, paramedic, data manager and lay representatives. The PMG will meet frequently during trial set up and approximately quarterly thereafter.

Data Monitoring and Ethics Committee

An independent DMEC will be organised during the study set up period in accordance with CTRU SOPs. The DMEC will review emerging data and adverse event reports and will ensure that the safety, rights and well-being of study participants are upheld throughout the study. Specific roles will include:

- Approval of the study protocol
- Review and approval of the SAP
- Evaluate interim data
- Review data collection, data linkage, and loss to follow up rates
- Consider emerging evidence from relevant studies
- Advise the SSC on whether there are any ethical or safety reasons why the study should not continue or protocol should be amended
- Advise the SSC on release of interim data

DMEC composition (Table 3) and conduct will be in accordance with CTRU SOP GOV003. An initial meeting will be held prior to the start of the trial and then approximately 6 monthly thereafter. No formal interim analyses are planned.

Patient and Public Involvement (PPI)

A public and patient advisory group will be enlisted for collaboration throughout the study. This group will be consulted on all aspects of study conduct, and help with specific tasks such as developing research materials and dissemination. The CI will liaise and mediate between the advisory group and the trial oversight groups, providing support where needed.

8. Publication and dissemination

The study protocol with be registered with an international research registry (ClinicalTrials.gov) and will be made available in the open access University electronic repository. Results of the study will be disseminated in high profile peer-reviewed scientific journals and relevant academic conferences. Authorship will include funded co-applicants, clinical collaborators, research paramedics and the study manager, according to International Committee of Medical Journal Editors (ICMJE) guidelines.

Details of the study, including regularly updated progress reports, will be available on a dedicated study website hosted by the CTRU. Plain English study progress reports will be provided to collaborators, patient advocacy groups, local PPI panels and our service user advisory group. Study developments will also be communicated through social media including twitter. The lay SMG member and service user advisory group will contribute to writing any scientific publications, particularly plain English summaries and conference presentations.

At the end of the study a report will be submitted to the trial funders with full details of study progress and study findings. It is anticipated that this report will be independently peer reviewed and the final accepted report published as a "gold" open access monograph in the *Health Technology Assessment* journal.

9. Finance

The study is funded by the NIHR Health Technology Assessment Programme (grant number 17/16/04). Details have been drawn up in a separate agreement.

10. Ethics approval

Phase 1 sub-studies, and Phase 3 sub studies on acceptability and usability of implemented triage tool do not involve patients and ethical approval will be confirmed with the University of Sheffield.

Phase 2 and 3 of the study will be conducted subject to a favourable opinion from a Local Research Ethics Committee (LREC), organised through the central National Research Ethics Service allocation system. An approval letter from the ethics committee will be registered with the CTRU before initiation of the study. Local research governance approvals will be sought from all participating research sites via the Health Research Authority (HRA). The study will be conducted in accordance with Good Clinical Practice Guidelines and CTRU SOPs.

11. Regulatory approvals

The MATTS validation and service evaluation studies will be conducted in compliance with a predefined protocol, HRA, CAG and REC approvals, Good Clinical Practice, CTRU SOPs, and the NHS research framework. Local research governance approvals will be sought from all participating research sites.

12. Indemnity / Compensation / Insurance

The MATTS project is sponsored by the University of Sheffield. The University holds insurance covering liabilities arising from negligent harm caused by poor protocol design by the Chief Investigator and researchers employed by the University. The participating ambulance services are covered by NHS indemnity for liabilities arising from clinical negligence, or other negligent harm to individuals taking part in the study where a duty of care is owed.

13. References

- 3. Coats TJ, Lecky F: 'Major trauma': now two separate diseases? *Emerg Med J* 2017, 34(8):494.
- 4. Vondy A, Willett K: Trauma care in England: London's trauma system goes live. *Emerg Med J* 2011, 28(3):250.

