Participating ambulance services estimate 150,000 calls for injury per 6 months across the included trauma networks, with TARN data suggesting that approximately 1,200 of these cases represent major trauma (ISS>15). Assuming, based on ASCOT criteria, a triage tool requires sensitivity of 95%, this sample size would provide a 95% confidence interval coverage of ±1.0% for the under-triage rate. Assuming a target specificity of 70% as per

ASCOT guidance, coding 3000 reference standard negative cases (sampling fraction of 2%) would give a 95% confidence interval coverage of $\pm 1.5\%$ for the over-triage rate.

Statistical analyses

The implemented triage tool will be scored using observed data, the presence of a trauma pre-alert recorded, and the actual transport destination collected. Compliance and real life performance of the implemented triage tool will subsequently be assessed. The reference standard will be the MATTS expert consensus definition of trauma with the potential to benefit from MTC care. Under/over-triage, sensitivity, specificity, predictive values, and c-statistics with their 95% confidence intervals (95% CI), will be calculated. The compliance of paramedic transport decisions with triage protocol results will be examined as a proportion with 95% CI. A priori sub-group analyses will examine tool performance in children and the elderly; and in penetrating and urban injury victims.

Safety reporting

In the MATTS Phase Three service evaluation study an optimal candidate triage tool will be voluntarily implemented by participating trauma networks. Adverse changes in the health of patients will be defined, monitored, recorded and reported according to CTRU SOP PM004 and Health Research Authority guidance for non-CTIMP studies. Adverse events (AEs) and serious adverse events (SAEs) related to major trauma triage will be recorded and reported. Table 1 details the definitions used.

Identification

Adverse health changes will be identified by paramedics during implementation of the triage tool and by research paramedics' review of EMS and hospital records. AEs will also be detected through review of ambulance service, hospital and trauma network incident reporting processes. Furthermore local investigators will report any additionally identified adverse health changes.

Management

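### Section 6.2.2 describes only the eligible cases in which the tool was not applied, so it cannot separate characteristics associated with non-use from the general case mix of eligible patients

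*Protocol*

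**What the plan says.** The first of the three approaches in section 6.2.2 concerns use of the tool. Its denominator is all eligible patients; the protocol will measure "what proportion of eligible patients (identified using the MATTS expert consensus definition) were recorded as assessed using the trauma triage tool".

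The one contrast stated for tool use is between ambulance services: "Overall and individual service rates will be calculated to establish if there are any between service differences".

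The characteristics analysis then narrows to one group: "For cases identified as eligible but where the tool was not applied we will conduct descriptive analyses of patient, incident type and injury variables". Its purpose is "to assess if there are any common characteristics which may help further refine the tool". The section's opening paragraph gives the wider aim: "Barriers to triage tool implementation, and targets to improve future performance, will also be identified".

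Section 6.1 contains two related analyses, but neither asks whether the tool was applied. The sub-groups concern accuracy: "A priori sub-group analyses will examine tool performance in children and the elderly; and in penetrating and urban injury victims". Compliance concerns where patients were taken: "The compliance of paramedic transport decisions with triage protocol results will be examined as a proportion with 95% CI".

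**The concern.** The protocol fixes both the group to be described (non-use cases) and the criterion (features they share). That criterion does not match the aim. A feature frequent among all eligible patients will be frequent among non-use cases even if crews apply the tool to those patients as often as to anyone else. A feature that is uncommon but strongly associated with non-use may attract no attention.

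At stake is where refinement effort goes. The findings of section 6.2.2 feed a stakeholder workshop and a toolkit for other services. Of the three approaches, this is the only one that uses patient-level records of non-use.

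**Working it through.** The protocol gives no sample size, expected non-use rate or precision for this analysis, so it has no figure to reproduce. The check is whether the share of a trait among non-use cases can be interpreted on its own.

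**Inputs**
- From section 6.1: about 1,200 major trauma cases over six months. This counts ISS>15, whereas eligibility in section 6.2.2 is the consensus definition, so it is a stand-in.
- From the Scientific Summary, Phase Three: reference standard positive cases are a census, about 300 per network.
- Assumed, not in the protocol: overall non-use u = 20% (10% and 40% as a range), and all trait shares and risk ratios below.

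**Formulas.** Let q be the trait's share of all eligible cases and RR the risk of non-use with the trait divided by the risk without it.
- Risk of non-use without the trait: r0 = u / (q·RR + 1 − q). With the trait: r1 = RR·r0.
- Share among not-applied cases: q·RR / (q·RR + 1 − q).
- Share among applied cases: q·(1 − r1) / (1 − u).

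The not-applied share depends on q and RR together. Seen alone, it cannot tell them apart. It does not depend on the number of cases, so a larger sample does not help.

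**Results at u = 20%**

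| Trait | Share, not applied | Share, applied | Non-use with v without trait |
|---|---|---|---|
| q = 50%, RR = 1.0 | 0.50/1.00 = 50.0% | 50.0% | 20.0% v 20.0% |
| q = 50%, RR = 0.8 | 0.40/0.90 = 44.4% | 51.4% | 17.8% v 22.2% |
| q = 5%, RR = 2.0 | 0.10/1.05 = 9.5% | 3.9% | 38.1% v 19.0% |

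The planned analysis shows only the first results column. In it, a trait with no association and a trait that makes non-use less likely both look far more prominent than the one that doubles the risk. The last two columns put the three traits in the right order.

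**A stronger association.** Take a trait in 5% of cases, with non-use of 60% against 18% in the rest (RR = 0.60/0.18 = 3.3). Its share of non-use cases is 0.05×0.60 / (0.05×0.60 + 0.95×0.18) = 0.030/0.201 = 14.9%. It could still be overlooked.

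**Would a comparison be informative?** With 1,200 eligible cases and 20% non-use, the groups are 240 and 960. For a trait present in about 60%, the SE of the difference is √(0.6×0.4×(1/240 + 1/960)) = 0.0354. Power for a 10-point difference is Φ(0.10/0.0354 − 1.96) ≈ 81% (two-sided 5%). From a 50% share, the difference detectable with 80% power is about 13, 10 or 8 points at 10%, 20% or 40% non-use.

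By service the numbers are thin for rare traits. A 5% trait gives 1,200×0.05 = 60 cases overall but 300×0.05 = 15 per network. At 60% non-use the 95% CI half-width is 1.96×√(0.24/60) = 12 points overall and 1.96×√(0.24/15) = 25 points per network.

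**The case against.** **The protocol does not rule out a comparison.** It does not say that only non-use cases will be described, the applied cases are already in the denominator, and table layout is normally left to the statistical analysis plan, which is not at hand. This stands in part: the plan may add the comparison. But the protocol names the group and the criterion, and followed as written it produces no reference column. That is more than an open detail.

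**No reasons are promised.** A reader might infer that the study will present ordinary case mix as the reasons for non-use. The protocol does not support that. It speaks of shared features that may help refinement and claims no causes. The supportable statement is that the analysis cannot distinguish the two.

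**Other evidence is available.** A clinician survey, triangulated with the Phase One focus groups, and a workshop that sets priorities also inform the toolkit, and readers may know the background case mix. This lowers the risk of misdirection. It does not repair the analysis, because neither activity measures non-use by patient characteristic.

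**Frequency matters too.** This stands. With 1,200 eligible cases, a group making up 60% with 20% non-use contributes 1,200×0.60×0.20 = 144 missed uses. The 5% trait with 60% non-use contributes 1,200×0.05×0.60 = 36. Frequency shows where most missed uses lie and should not be discarded in favour of relative risk.

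**The magnitudes are assumed.** This also stands. They show the mechanism, not the size of an error in this study.

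**Conclusion.** The point holds in a limited form. As written, section 6.2.2 cannot distinguish characteristics associated with non-use of the tool from the case mix of eligible patients. The plan's own aim of identifying barriers and targets for improvement needs that distinction.

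The logic rests on an identity and needs no assumption about sample size. The sizes shown (50% for an unrelated common trait, 9.5% or 14.9% for rare but strong correlates) rest on assumed shares and non-use rates. The figure of 1,200 is an ISS>15 proxy.

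Severity is low. The analysis is ancillary and descriptive, and it does not enter the sensitivity, specificity, under/over-triage or transport-compliance estimates. The gap can be closed at any time before the analysis is reported.

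**What to change.** Replace the sentence in section 6.2.2 with one to this effect: patient, incident type and injury variables will be tabulated side by side for eligible cases in which the tool was applied and in which it was not, and the proportion not applied will be reported at each level of each variable with a 95% CI, overall and by ambulance service.

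Add that these proportions will be read alongside the number of non-use cases at each level, so that strength of association and volume of missed use are both visible. Rare levels should be interpreted overall rather than by service. A logistic model for non-use is optional and not needed to close the gap.

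Cost: one sentence in the protocol and slightly more descriptive analysis. No new data are needed, because the applied cases are already identified in the denominator.
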